Neuroscience-Informed Treatment Development for Adolescent Alcohol Use NCT03238300 November 30, 2022

Aim 1:

Hypothesis/aim	Primary: 1a. Quantify the effect of NAC versus placebo on glutamate levels in adolescent heavy drinkers. Using MRS, we will determine the effect of NAC versus placebo on modulating anterior cingulate glutamate levels in heavy alcohol-using adolescents. Hypothesis: Heavy drinking youth will show decreasing levels of glutamate from baseline in the anterior cingulate while on NAC compared to placebo.
Sample size for aim	N= 31 – all with 4 sessions (randomization visit 1, MRI visit 2 & 4, washout visit 3)
Independent variable(s)	NAC v. Placebo: both NAC and placebo were administered twice daily (2400 mg of NAC/day, administered as 1200 mg twice/day) over 10 days
Dependent variable(s)	dACC glutamate levels
Handling of missing data	Only participants with complete data will be included (N=31)
	Complete data = screener, visit 1-4
How outliers and excluded observations will be defined	Participants with all 4 sessions (visit 1-4) will be included. MRS data will be examined for quality using: 1. Linewidth (exclusion: >3 SD from mean) 2. Signal-to-noise ratio (SNR) (exclusion: >3 SD from mean)
	No other outliers will be removed.
Software and specific	Software: R
software modules or packages	Packages: Tidyverse, Imer4 OR glmer4 & ImerTest
Analytic procedure(s)	Generalized linear mixed effect models will examine the effect of NAC vs placebo on neurometabolites (Primary: glutamate) within the adolescent heavy drinking group.
	The primary model will contain the main effect of treatment (NAC vs. placebo), as well as day (period: scan 1 vs. scan 2) and order (sequence: NAC/placebo vs. placebo/NAC) to ensure the crossover design and washout period were successful.
	During model development, random intercepts will be included to account for variations in baseline response levels for individual participants (1 id)

	Covariance structure will be determined based on best fit after trying standard options (e.g., unstructured, Toeplitz, autoregressive, etc.) Model fit will be tested using likelihood ratio tests, Akaike Information Criterion values, and interclass correlation. Parameter estimates and associated 95% confidence intervals for treatment effects on DVs.
Steps to confirm data assumptions are met	Generalized linear effect mixed models -Check normality of data using Shapiro-Wilks test &/or QQ plot -Divide generalized chi-square by its degrees of freedom to check for dispersion -Compare averages of outcomes to predicted values to check appropriateness of link function -Transform data (if needed) -Check for multicollinearity among predictor variables -Check for carry over effect in crossover models
	Generalized linear models -Plot deviance residuals against fitted values to evaluate linearity for GLM -Look for outliers using leverage & Cook's distance &/or a QQ plot for GLM -Transform data if needed but only on predictor variables
A priori covariates and/or means for identifying important covariates	Baseline levels of clinical and demographic characteristics will be tested for univariate associations with study outcomes; when associated, these variables will be included in the adjusted model development strategy.
	Primary:
	• Age
	• Sex
	Alcohol use variables
	Exploratory:
	Cannabis use variables
A priori interactions to be examined and rules for retaining interaction terms	None.
Planned subgroup or sensitivity analyses	N/A
Level of significance and whether/what corrections for multiple testing will be used	P<0.05, no correction for multiple comparisons

(if null hypothesis significance testing is used)	
Required data	RedCap:
cleaning/formatting steps	 Download baseline variables Age Sex Group (drinker v. control) Mental health measures (anxiety, depression) Download drinking variables from TLFB Total drinking days (visit 1-4) Total drinks/drinking day (visit 1-4) Download other substance use variables from TLFB Total cannabis use days (visit 1-4) Total cannabis use/use day (visit 1-4)
	c. Total vaping days (visit 1-4) d. Total cigarette days (visit 1-4) MRS: 4. Combine excel spreadsheets for all visits and metabolites 5. Remove unnecessary variables a. Final variables: i. Metabolite levels (I.U.) ii. Linewidth iii. SNR Combine RedCap + MRS Data: 6. Merge RedCap and MRS data sheets 7. Remove participants without full data (final N=41) 8. Remove observations that don't meet criteria for inclusion

Aim 2:

Hypothesis/aim	Primary Aim #1: Aim: Quantify the effect of NAC versus placebo on alcohol cue reactivity in adolescent heavy drinkers Hypothesis 1: Heavy drinking youth with show decreasing alcohol cue reactivity from baseline in key reward regions (insula, striatum, and amygdala) while on NAC compared to placebo
Sample size for aim	Initial sample size: n = 31 (heavy drinkers; 17 female & 14 male) Sample size for complete data: n = 27 (14 female & 13 male)
Independent variable(s)	Medication: NAC vs. Placebo
Dependent variable(s)	Primary Aim #1: Primary contrast: BOLD response (alcohol v. non-alcohol cues) in 10 regions of interest (left and right): amygdala, insula, caudate, nucleus accumbens, and putamen
Handling of missing data	Multiple imputation will be used for missing data ('mice' package) on independent variables only.
How outliers and excluded observations will be defined	Participants with excess head motion (defined as mean relative motion >0.2 mm) and missing cue-reactivity data at baseline will be removed (n = 4). Outliers will be checked with Q-Q plots and examination of residuals.
Software and specific software	Software: R
modules or packages	Packages: Tidyverse, Irtest, LME, Performance
Analytic procedure(s)	 Generalized linear mixed effect model will examine the effect of NAC vs placebo on alcohol cue reactivity The primary model will contain the main effect of treatment (NAC vs. placebo), as well as day (scan 1 (visit 2) vs. scan 2 (visit 4)) and order (NAC/placebo vs. placebo/NAC) to ensure the crossover design and washout period were successful. During model development, random intercepts will be included to account for variations in baseline response levels for individual participants Model fit will be tested using likelihood ratio tests, Akaike Information Criterion values, and interclass correlation. Model based parameter estimates across groups (means and standard deviations) will be used to estimate treatment effect sizes
Steps to confirm data assumptions are met	Check for normality of data with Q-Q plot Check for appropriate link function by comparing averages of outcomes versus predicted values Check for overdispersion by dividing generalized chi-square by degrees of freedom. Check for multicollinearity among predictors with VIF (cut-off of 2)
A priori covariates and/or means for identifying important	Day and Order will be included in all models.
covariates	Aim #1 and exploratory covariates: Baseline BOLD response (alcohol v. non-alcohol cues) in relevant region of interest (i.e. in models with ACC as the outcome, BOLD response at baseline in ACC will be the covariate), alcohol use (average standard drinks per drinking day, total quantity of standard drinks, number of drinking days, and number of binge episodes), AUD status (Yes/No defined by meeting DSM-5 criteria at screening) or AUD severity (none, mild, moderate, or severe defined by DSM-5 criteria at screening), cannabis use days, age, sex, and race.

A priori interactions to be examined and rules for retaining interaction terms	'Performance' package will be used to determine best fitting model with select covariates to reduce issues related to multicollinearity – only 1 alcohol covariate will be used, and will be specific to each model N/A
Planned subgroup or sensitivity analyses	Sensitivity analysis will compare results from complete data only model (n = 27) and imputed model (n = 31) to confirm the imputed data does not significantly change the results.
Level of significance and whether/what corrections for multiple testing will be used (if null hypothesis significance testing is used)	p < 0.05, no correction for multiple comparisons
Required data cleaning/formatting steps	 Complete second-level cue-reactivity data processing in Freesurfer and extract relevant data for models (average percent change in BOLD signal between alcohol vs. non-alcohol cues from the ROIs) Download data for covariates from Redcap and look at descriptive statistics to assess accuracy and distributions Download raw TLFB data from Box Calculate TLFB summary variables: average standard drinks per drinking day, total quantity of standard drinks, number of drinking days, and number of binge episodes during 10-days on treatment
	 5. Combine data from Redcap and output from fMRI preprocess pipeline and Freesurfer 6. Complete multiple imputation for missing data 7. Run models on imputed dataset and completers only dataset to check for any differences

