Heavy-drinking youth display robust activation in reward regions during the Alcohol Cue Reactivity Task. In a pilot study using the same fMRI alcohol cue reactivity task proposed for this application (Schacht et al. 2011), 11 heavy drinking youth displayed robust activation in several brain regions including the anterior cingulate, insula, striatum, and amygdala during alcohol vs. non-alcohol cue trials (see Figure 1), which is highly consistent with activation patterns seen in adult studies (Schacht et al. 2013a). Understanding the role of NAC on reducing cue reactivity as well as glutamatergic levels (via MRS) will be the primary aims of this application.

Intervention to be studied

PHARMACOLOGICAL INTERVENTION

This double-blind crossover trial will compare NAC (1,200mg twice daily) and placebo. If assessment procedures reveal that a participant meets inclusion criteria and none of the exclusion criteria, the participant will be randomized to each condition for 10 days in a counterbalanced order. There will be a minimum 11-day washout period between conditions to allow for the clearance of NAC (Holdiness 1991). Medication response and tolerability/adverse events will be assessed at each clinic visit. Medication videos will be uploaded by participants to track medication compliance. Reminders to take medication will be sent via email or text message to increase compliance. Primary mentor [name] has a current IND for using NAC with adolescent substance users (#78,927).

Study personnel will review medication logs and data from the Medication Event Monitoring System (MEMSCapTM) that track when the pill bottles are opened, as well as perform pill counts throughout treatment to monitor medication adherence. Medication tolerability and effects will be systematically assessed. Participants will be encouraged to contact study personnel between visits to address any immediate concerns regarding adverse effects. If a participant experiences intolerable medication-related adverse effects at any point during the study, a dose reduction to 600 mg twice daily may be undertaken. The dosage may be increased back to 1200 mg twice daily at the discretion of the medical clinician. However, if a participant is unable to tolerate the reduced dose, medication will be discontinued, and the participant will continue to come in for study visits.

Inclusion and Exclusion Criteria/ Study Population

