Sample Size Determination. Crossover designs are highly cost-efficient and powerful designs (Wellek and Blettner 2012). Previous research has shown NAC has an effect size of d =1.13 versus placebo on glutamatergic levels in the ACC in cocaine dependent adults in a similar randomized, double-blind, placebo-controlled within-subjects crossover study (Schmaal et al. 2012). With 32 participants, the proposed study will have 85% power to detect such effects (α = 0.05, two-tailed) (Erdfelder et al. 1996). Having 50 heavy drinking participants will allow for 20% participant drop out, which is consistent with the drop out rate at the 4 week mark in [name] NAC adolescent marijuana trial, as well as exclusion of participants due to motion in scanner (Gray et al., 2012).

Analysis and approach. (1) BOLD response to alcohol vs. non-alcohol cues in the regions of interest (ACC, insula, striatum, amygdala) and (2) glutamate levels in the ACC will be the primary contrasts of interest to test Aims 1 and 2. A generalized linear mixed effect model will examine the effect of NAC vs placebo on alcohol cue reactivity and glutamate. The primary model will contain the main effect of treatment (NAC vs. placebo), as well as day (scan 1 vs. scan 2) and order (NAC vs. placebo) to ensure the crossover design and washout period were successful. During model development, random intercepts will be included to account for variations in baseline response levels for individual participants and random slopes to account for varying responses to treatment. Model fit will be tested using likelihood ratio tests and Akaike Information Criterion values. Baseline levels of clinical and demographic characteristics (sex, age, alcohol use characteristics) will be tested for univariate associations with study outcomes; when associated, these variables will be included in the adjusted model development strategy. Parameter estimates and associated 95% confidence intervals for treatment effects on cue reactivity and glutamate will be reported. Model based parameter estimates across groups (means and standard deviations) will be used to estimate treatment effect sizes, in order to inform power analysis for a subsequent full-scale randomized controlled trial. Power analyses and predetermined statistical analyses will ensure findings are robust and unbiased.

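### A non-significant order term cannot show that the washout worked: with 31 people it would miss a carryover that halves the NAC effect 53–64% of the time, taking the protocol's d = 1.13 in SD units

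*SAP*

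**What the plan says.** SAP Aim 1 (glutamate), Analytic procedure(s), fits treatment, day and order with a random intercept per participant. It gives the purpose of day and order as "to ensure the crossover design and washout period were successful". The same clause appears in SAP Aim 2 (cue reactivity), Analytic procedure(s), and in the protocol under Analysis and approach. The Aim 1 assumption checks add "Check for carry over effect in crossover models", without a method, a threshold or a consequence.

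The Aim 1 sample is fixed by "Only participants with complete data will be included (N=31"; the criterion is "P<0.05, no correction for multiple comparisons". Sensitivity analyses are marked not applicable in Aim 1. In Aim 2 the only one compares complete with imputed data.

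The protocol's section on the intervention supports the washout on pharmacokinetic grounds: "There will be a minimum 11-day washout period between conditions to allow for the clearance of NAC". The neuroimaging section schedules three scans, one at baseline and one after each condition. None falls at the end of the washout.

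**The concern.** In a two-period crossover with a random intercept, order is tested between people. It picks up carryover, but also any chance difference between the two sequence groups. A significant result does not show that the washout failed, and a non-significant one does not show that it worked. Neither document states how large a carryover the check should exclude, or how likely it is to find one.

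Carryover of NAC into a following placebo period pulls the treatment estimate towards zero. The risk is a weakened or null NAC result reported beside a reassurance about the washout that the data cannot give. The protocol also means to use these effect estimates to power a later trial, so an unrecognised attenuation would carry forward.

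**Working it through.** **Inputs from the documents.** N = 31 (SAP Aim 1), taken as two-sided α = 0.05; planning effect d = 1.13 (protocol, Sample Size Determination).

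**Assumptions.** A 15/16 split between sequences; equal variances; carryover L only from NAC into a following placebo period; correlation ρ between any two scans of one person, from 0.3 to 0.8. The documents give no ρ. They also do not say whether d is in between-person SD units or in units of the SD of paired differences.

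**The plan's own figure.** The protocol states: "Previous research has shown NAC has an effect size of d =1.13 versus placebo on glutamatergic levels in the ACC" and "With 32 participants, the proposed study will have 85% power to detect such effects (α = 0.05, two-tailed". A two-sample t-test at d = 1.13 gives 84.8% power with 15 per group and 87.1% with 16 per group. So 32 is the smallest equal-group total that reaches 85%. A paired test with d = 1.13 in SD-of-difference units and 32 people has over 99.9% power. The stated N thus fits d in SD units, though the text does not say so.

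**Bias.** The two-period treatment estimate is half the difference between sequences in the mean within-person change. With true effect τ, carryover shifts it to τ − L/2. Halving needs L = τ. With L = τ/2 the estimate falls by a quarter (1.13 to 0.85).

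**Order test.** The contrast of person means between sequences is L/2. A person mean has SD √((1+ρ)/2), so the standardised effect is e = L/√(2(1+ρ)). The noncentrality is e/√(1/15 + 1/16) = e/0.3594, with 29 df. For L = 1.13 and ρ = 0.5: e = 1.13/√3 = 0.652, noncentrality 1.82, power 42%, miss rate 58%.

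**Confidence interval for L.** The half-width is 2 × √((1+ρ)/2) × 0.3594 × 2.045. Adjusting for a baseline scan with the same ρ replaces the SD by √((1+ρ)/2 − ρ²) and the t value by 2.048 (28 df). At ρ = 0.5: 2 × 0.866 × 0.3594 × 2.045 = 1.27, and adjusted 2 × 0.707 × 0.3594 × 2.048 = 1.04.

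| ρ | Miss rate, L = 1.13 SD | Miss rate, L = 0.5 SD | 95% CI for L, unadjusted | 95% CI for L, baseline-adjusted |
|---|---|---|---|---|
| 0.3 | 53% | 87% | ±1.19 SD | ±1.10 SD |
| 0.5 | 58% | 88% | ±1.27 SD | ±1.04 SD |
| 0.7 | 62% | 89% | ±1.36 SD | ±0.88 SD |
| 0.8 | 64% | 89% | ±1.40 SD | ±0.75 SD |

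**The other reading of d.** In SD-of-difference units, e = 1.13 × √((1−ρ)/(1+ρ)). The miss rate is then 39% at ρ = 0.3, 58% at 0.5, 75% at 0.7 and 83% at 0.8.

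**Smaller carryover.** With d = 1.13 SD and L = 0.565 SD (half the effect), the miss rate is 86–87% at ρ 0.5 to 0.8.

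**Joint consequence.** For a true effect of 0.5 SD (assumed) at ρ = 0.5, power for treatment is about 77% without carryover. If carryover halves the estimate to 0.25 SD, power is about 27%, and the order test stays silent about 88% of the time.

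**The case against.** The strongest reply is that the plan's real protection is the washout, not the test. If the second scan follows a 10-day placebo course after at least 11 days off drug, it comes roughly 11 + 10 = 21 days or more after the last NAC dose. A carryover equal to the whole effect is then implausible. This stands: halving is an extreme case, and the documents do not support an inference that carryover is present or that the washout fails. It does not rescue the order term, because smaller carryovers are missed more often.

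A reader might infer that the check fails almost nine times in ten. That needs a true effect near 0.5 SD, or d = 1.13 in SD-of-difference units with ρ about 0.9. The documents give neither.

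A reader might also infer that a non-significant order term will be reported as proof of a successful washout. No sentence says so. The Aim 1 carryover check has no stated method, so the order p-value cannot be called the only check. But with no end-of-washout scan, any check on the imaging outcomes has to compare the two sequence groups, and meets the same limits.

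Nor is the baseline scan ignored throughout. Baseline glutamate is not a named covariate in SAP Aim 1, but SAP Aim 2 lists baseline BOLD response in the relevant region as a candidate. Adjustment does help: at d = 1.13 in SD units it raises the order test's power to 57%, 72% and 85% at ρ = 0.5, 0.7 and 0.8.

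Finally, the plan contains no rule to pretest for carryover and drop period 2. The two-period estimate is already the planned one, which is to its credit.

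**Conclusion.** The point holds in a limited form. The purpose clause gives the order term a task that it cannot perform in this design, whatever the effect size, because carryover and chance group differences cannot be separated. At N = 31 the test is also weak: it misses a halving carryover 53–64% of the time at d = 1.13 in SD units, and 87–89% at an assumed effect of 0.5 SD. Under the SD-of-difference reading the miss rate exceeds one half only at the higher correlations examined (0.5 and above). The unadjusted interval of about ±1.2 to 1.4 SD is wider on each side than the whole planned effect, if that is in SD units. These figures rest on the 15/16 split, equal variances and the assumed correlations. The evidence supports a correction to what the trial may conclude about its washout. It does not show that the NAC estimate is biased.

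**What to change.** - Keep day and order as design terms in all three places, but delete the claim that they ensure success. State that no conclusion of a successful washout will be drawn from a non-significant order term, and rest the washout on its pharmacokinetic rationale.
- Report the order/carryover estimate with its 95% CI, adjusted for the baseline scan. For Aim 1 this means naming baseline glutamate as a covariate; for Aim 2, fixing baseline BOLD in this model instead of leaving it to model selection.
- Add one sensitivity analysis per outcome: NAC versus placebo in period 1 only, adjusted for the baseline scan. Carryover between treatment periods cannot affect it.

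The cost is SAP wording and one extra model per outcome on data already collected. The period-1 estimate is less precise. At ρ = 0.5 its 95% half-width is √(1 − 0.25) × 0.3594 × 2.048 = 0.64 SD, against 0.5 × 0.3594 × 2.045 = 0.37 SD for the two-period estimate. Its power for a 0.5 SD effect is about 29–47% at ρ 0.3 to 0.7. It should support the two-period estimate and not replace it.

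### SAP Aim 2 leaves the time window of its alcohol covariate unclear, and the only step that computes the same measures appears to use drinking on treatment

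*SAP*

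**What the plan says.** SAP Aim 2 covers alcohol cue reactivity, which is Aim 1 in the protocol. Its primary model contains treatment, "as well as day (scan 1 (visit 2) vs. scan 2 (visit 4)) and order (NAC/placebo vs. placebo/NAC"). Day and order stay in every model.

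The row on a priori covariates opens with the word Baseline, attached to BOLD response, and then lists "alcohol use (average standard drinks per drinking day, total quantity of standard drinks, number of drinking days, and number of binge episodes"), followed by AUD status or severity, cannabis use days, age, sex and race. BOLD response is tied to baseline a second time in its own bracket, and AUD is tied to screening. The alcohol measures have no such tag. On selection, the SAP says that the "Performance' package will be used to determine best fitting model with select covariates", with a single alcohol covariate that may differ from model to model.

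The data steps for Aim 2 include "Download data for covariates from Redcap and look at descriptive statistics to assess accuracy and distributions", then "Download raw TLFB data from Box", then a calculation of the four alcohol summaries that ends "number of drinking days, and number of binge episodes during 10-days on treatment". The merge step reads "Combine data from Redcap and output from fMRI preprocess pipeline and Freesurfer".

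In the protocol, Analysis and approach says that baseline characteristics, alcohol use among them, are the candidates for adjustment. The Exploratory Aim treats drinking during the NAC and placebo periods as an outcome. It expects no large change but anticipates a possible fall on NAC. Self-report measures describes a 90-day TLFB taken before the intervention.

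**The concern.** The list in the covariate row and the list in the calculation step hold the same four measures in the same order. No Aim 2 step computes a pre-intervention version. An analyst who follows the steps literally would take the on-treatment summaries as the alcohol covariates.

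Those values arise after randomisation, and the protocol itself thinks NAC may lower them. Adjusting for them would remove any part of the NAC effect that runs through drinking. It could also create an apparent effect if drinking and BOLD response share unmeasured causes within a period. The alcohol covariate is chosen by fit, model by model, so the adjustment could differ across the ten regions of interest. The SAP does not say which model supplies the treatment effect sizes, and the protocol wants those for planning a later trial.

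**Working it through.** **1. What the text settles.** The documents give no figure for this point, so there is none to reproduce. The check is a comparison of passages.

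| Item | Window stated |
|---|---|
| BOLD covariate, SAP Aim 2 | Baseline |
| AUD covariate, SAP Aim 2 | Screening |
| Alcohol covariates, SAP Aim 2 | None of their own |
| Calculation of the same four measures, SAP Aim 2 | 10 days on treatment |
| Covariate rule, protocol | Baseline, alcohol use included |

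The SAP also does not say whether the on-treatment summary is one value per period or one per person.

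**2. When the window can matter.** Both scans come from the same person, so the NAC–placebo contrast is a within-person difference. A covariate with one value per person cancels from that difference. In simulated 2×2 crossovers with a random intercept and terms for treatment, day and order (N=31 and N=27), adding baseline drinking, or on-treatment drinking averaged over both periods, left the treatment estimate unchanged in every replicate (largest difference below 1e-15). Only a period-specific value can move it, by

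change in estimate = covariate coefficient × shift in drinking due to NAC.

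**3. Size under assumed inputs.** The documents give no effect size for drinking and no link between drinking and BOLD response. Every input here is an assumption, in one-period within-person SDs. With within-person SD 1, the standard error of the contrast is √(2/N): √(2/31) = 0.254 and √(2/27) = 0.272.

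*A. No true NAC effect on BOLD.* The assumed within-person correlation of drinking and BOLD is 0.25 and the between-person correlation is 0 or 0.25. The mean fitted coefficient is then 0.17 or 0.25. At N=31:

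| Shift in drinking | Change in estimate | Change ÷ 0.254 | Simulated type I error |
|---|---|---|---|
| 0.1 | 0.017–0.025 | 0.07–0.10 | 4.9–5.3% |
| 0.25 | 0.043–0.062 | 0.17–0.25 | 5.3–6.0% |
| 0.5 | 0.085–0.125 | 0.33–0.49 | 6.8–7.7% |

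The simulation used 6,000 replicates (Monte Carlo error about 0.3 points). The unadjusted model gave 4.4–5.6%, so the first row cannot be told apart from no effect.

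*B. Drinking as a true mediator.* The assumed direct effect is −0.30 and the slope of BOLD on drinking is 0.3 to 0.5. The share of the total effect removed is slope × shift ÷ (0.30 + slope × shift):

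- Shift 0.1: 0.03/0.33 = 9% to 0.05/0.35 = 14%.
- Shift 0.25: 0.075/0.375 = 20% to 0.125/0.425 = 29%.
- Shift 0.5: 0.15/0.45 = 33% to 0.25/0.55 = 45%.

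If the shift is zero, nothing is removed.

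**The case against.** A reader might infer that the SAP plans to adjust its main NAC result for drinking measured after randomisation. The documents do not support that, for five reasons.

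- Baseline at the head of the row may govern the whole list. The separate tags for BOLD and AUD make this the weaker reading, but it is open. If it is right, the row still does not match the calculation step.
- Covariates have their own RedCap download, and the merge step names RedCap and imaging output but not Box, where the raw TLFB data sit. Cannabis use days, also a TLFB measure, is in the covariate row but is not computed in the TLFB step. The listed steps therefore do not derive every TLFB covariate, and the lack of a baseline calculation is weak evidence. Aim 1 also places TLFB measures under RedCap ("Download drinking variables from TLFB Total drinking days (visit 1-4")). That entry spans visits 1 to 4 and sits apart from the baseline variables, so it does not supply a baseline window.
- The on-treatment summaries may be meant for the exploratory drinking aim. That aim names only two of the four measures, but the covariate row also serves exploratory models.
- The treatment-days window may attach only to binge episodes. The other three measures would then have no window at all.
- The planned comparison of imputed and complete data (n=31 against n=27) implies that covariate models exist. The exclusions behind it are head motion and missing baseline cue-reactivity data, so it points to baseline BOLD and says nothing about drinking.

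It is also fair to say that the larger figures need a 0.5 SD shift, while the protocol expects no dramatic change in drinking. A baseline drinking covariate would leave the contrast where it is, so the gain from the fix is avoiding bias, not precision.

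These points rule out calling this a demonstrated error. They do not supply the missing window: each reading leaves the alcohol covariate undefined or at odds with the calculation step.

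**Conclusion.** The point holds as an unclear covariate window with one harmful reading, not as a proven plan to adjust for on-treatment drinking. Harm requires that the on-treatment summaries are the covariates, that they enter as one value per period, that NAC changes drinking, and that drinking is related to BOLD response within a person. Under those conditions the covariate-adjusted estimate departs from the total randomised effect and from the protocol's baseline rule. The treatment/day/order model is not affected. The actual size cannot be derived from the documents. The ranges above only illustrate it and depend on the chosen inputs: small for small shifts in drinking, material only for large ones. Severity is minor to moderate, with moderate confidence.

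**What to change.** 1. In the Aim 2 covariate row and calculation step, define the alcohol covariate from the pre-intervention TLFB and state the window (the protocol's baseline instrument covers 90 days).
2. State that the reported NAC effect and the effect sizes come from the treatment/day/order model already named primary, with covariate-adjusted models as supporting.
3. Assign the on-treatment summaries to the exploratory drinking outcome, or to an analysis labelled as mediation.

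The cost is SAP wording and one different TLFB summary, from data already collected. The downside is that the supporting models lose adjustment for recent drinking.
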